# 4.2

## 4.2.1

Primary endpoint analysis Definition of endpoint(s) Itcome variable is the proportion The primary outcome variable is the proportion of study participants able to successfully selfadminister rozanolixizumab using both syringe driver and the manual push method, respectively, during the Self-administration Periods Successful self-administration includes a correct SC infusion with the intended dose at the correct infusion site by the participant. Treatment success will be defined as a successful self-administration at the last dose of self-administration using the ] for Sequence 1 and Visit 19 syringe driver (Visit 13 ] for Sequence 2) or via manual push (Visit 19 [( for Sequence 1 and Visit 13 [ for Sequence 2).

#### 4.2.2 Main analytical approach

The number and proportion of participants deemed a treatment success will be tabulated separately by period and overall for each self-administration method for the FAS.

The proportion of success together with its 90% CI will be estimated for each self-administration with syringe driver and manual push overall using the Wilson method (without continuity correction) [2]. The Wilson method was selected rather than the Clopper Pearson exact method due to a larger number of participants able to perform self-administration using both methods than planned in Section 5.

In case at least one of the three questions related to the administration is missing (correct infusion site, subcutaneous, intended dose), the self-administration is considered unsuccessful.

The self-administration data will be listed for the SS including the training information.

Stion

#### 4.2.3 Sensitivity analyses

A sensitivity analysis will be performed using the same analytical approach as for the primary endpoint, but reporting the data collected for RSS.

#### 4.3 Secondary endpoints analysis

#### 4.3.1 Secondary endpoints

#### 4.3.1.1 Definition of endpoint(s)

The secondary endpoints are:

- Occurrence of TEAEs after syringe driver or manual push self-administration from Visit 2 up to the End of Study Visit (Visit 21 [Week 26]).
- Occurrence of local site reactions up to 24 hours after each administration during the Training Period and Self-administration Periods.
- Occurrence of medication errors associated with adverse reactions during the 2 Selfadministration Periods of the study.)

A TEAE is defined as an AE starting on or after the date of first administration of rozanolixizumab in the study, up to and including 8 weeks (56 days) after the final dose.

A TEAE will be assigned to the Training period if the start date of the event is on or after the date of the first administration of rozanolixizumab during the Training Period and before the date of first administration of rozanolixizumab in Self-administration Period 1.

A TEAE will be assigned to the Self-administration Period 1 if the start date of the event is on or after the date of the first administration of rozanolixizumab in Self-administration Period 1 and before the date of the first administration of rozanolixizumab in Self-administration Period 2.

A TEAE will be assigned to the Self-administration Period 2 if the start date of the event is on or after the date of the first administration of rozanolixizumab in Self-administration Period 2 and up to the end of Visit 20 assessments (EOT date).

Where dates are missing or partially missing, AEs will be assumed to be treatment-emergent unless evidence exists that does not allow the AE to be treatment-emergent. Handling of missing dates for classification of AEs as TEAEs is described in Section 4.1.8.

The local site reactions up to 24 hours after each administration are defined as AEs reported as local site reactions as per CRF within one day after rozanolixizumab administration.

Medication errors associated with adverse reactions are defined as the AEs whose preferred terms belong to the Standardised MedDRA Queries (SMQ) "Medication errors" and leading to adverse reactions.

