8.3.7 Medication errors associated with self-administration

The definitions of medication errors can be found in Appendix 12 (Section 10.12). The medication errors reported by the study participant (or, when appropriate, by a caregiver, or observed by the investigator) shall be recorded in the paper Medication Error form by the investigator and emailed to the Global mailbox: [contact]. The fax and mobile number are also provided in case of urgent necessity. All medication errors except those considered as AESM (see Section 8.3.8) will be recorded and reported to the sponsor or designee within 7 days of awareness. Medication errors that are considered AESM (see Section 8.3.8) will be recorded and reported within 24 hours following the SAE recording and reporting procedures as indicated in Appendix 3 (Section 10.3) and using the Medication Error form. If the medication error is observed from other periods of the study (apart from Self-administration Periods), the medical monitor should be informed for further advice.

The investigator and any designees are responsible for detecting, documenting, and recording events that meet the definition of a medication error and remain responsible for following up medication errors that are considered AESM (see Section 8.3.8).

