8.3.8 Adverse events of special monitoring

An AESM is a product-specific AE, adverse reaction, or safety topic requiring special monitoring by UCB.

For rozanolixizumab, the following events require immediate reporting (within 24 hours regardless of seriousness) to UCB:

- Severe and/or serious headache
- Suspected aseptic meningitis
- Medication error associated with adverse reaction(s)

Procedures for the management of AESM are provided in Appendix 14 (Section 10.1

tion 10.14) Although infections and hypersensitivity reactions including infusion-related reactions and anaphylaxis are not classified as AESM, these AEs will be monitored by the investigator. If such an event is suspected, it should be managed according to the guidance provided in Appendix 13 (Section 10.13). Suspected anaphylaxis reactions should be diagnosed using Sampson's Criteria (Sampson et al, 2006).

All AESM will follow the SAE recording and reporting procedures as indicated in Appendix 3 (Section 10.3). Medication error associated with adverse reaction(s) should also be assessed, recorded, and reported using the Medication Error form as indicated in Section 8.3.7.

8.3.9 Medical device - adverse events (ADEs, unanticipated ADEs, SAEs, SADEs, and unanticipated SADEs) and device deficiencies

Medical devices are being provided for administration of IMP in this study. In order to fulfill regulatory reporting obligations worldwide, the investigator is responsible for the detection and documentation of events meeting the definitions of ADEs, SADEs, and device deficiencies that occur during the study with such devices.

Adverse events will be reported according to the ISO 14155:2020, while recognizing and following requirements including reporting timelines specified in other specific laws, regulations, directives, standards and/or guidelines as appropriate and as required by the countries in which the clinical investigation is conducted.

The definition of an ADE, SADE, and device deficiency can be found in Appendix 7 (Section 10.7).

NOTE: Events fulfilling the definition of an AE or SAE will also follow the processes outlined in Section 8.3.3 and Appendix 3 (Section 10.3) of the protocol.

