8.5 Treatment of overdose

Unintentional overdose events are considered Medication Errors and should be reported as described in Section 8.3.7 and Section 8.3.8.

However, in the event of an overdose, the investigator or treating physician should:

- 1. Contact the medical monitor immediately.
- 2. Closely monitor the participant for any AE/SAE and laboratory abnormalities for at least 5 days.
- 3. Obtain a plasma sample for pharmacokinetic analysis within 72 hours from the date of the last dose of study medication if requested by the medical monitor (determined on a case-by-case basis).
- 4. Document the quantity of the excess dose as well as the duration of the overdose in the CRF.

Decisions regarding dose interruptions will be made by the investigator in consultation with the medical monitor based on the clinical evaluation of the participant.

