- Exacerbation of a chronic or intermittent pre-existing condition, including either an increase in frequency and/or intensity of the condition.
- New conditions detected or diagnosed after study medication administration even though it may have been present before the start of the study.
- Signs, symptoms, or the clinical sequelae of a suspected drug-drug interaction.
- Signs, symptoms, or the clinical sequelae of a suspected overdose of either study medication or a concomitant medication. Overdose per se will not be reported as an AE/SAE unless it is an intentional overdose taken with possible suicidal/self-harming intent. Such overdoses should be reported regardless of sequelae.
- "Lack of efficacy" or "failure of expected pharmacological action" per se will not be reported as an AE or SAE. Such instances will be captured in the efficacy assessments. However, the signs, symptoms, and/or clinical sequelae resulting from lack of efficacy will be reported as AE or SAE if they fulfill the definition of an AE or SAE.
- The signs, symptoms, and/or clinical sequelae resulting from lack of efficacy will be reported as AE or SAE if they fulfill the definition of an AE or SAE. Also, "lack of efficacy" or "failure of expected pharmacological action" also constitutes an AE or SAE.

Events **NOT** meeting the AE definition

- Any clinically significant abnormal laboratory findings or other abnormal safety assessments which are associated with the underlying disease, unless judged by the investigator to be more severe than expected for the participant's condition.
- The disease/disorder being studied or expected progression, signs, or symptoms of the disease/disorder being studied, unless more severe than expected for the study participant's condition.

Confidential Page 70 of 124

- Medical or surgical procedure (eg, endoscopy, appendectomy): the condition that leads to the procedure is the AE.
- Situations in which an untoward medical occurrence did not occur (social and/or convenience admission to a hospital).
- Anticipated day-to-day fluctuations of pre-existing disease(s) or condition(s) present or detected at the start of the study that do not worsen.

Definition of SAE

If an event is not an AE per definition above, then it cannot be a SAE even if serious conditions are met (eg, hospitalization for signs/symptoms of the disease under study, death due to progression of disease).

A SAE is defined as any untoward medical occurrence that, at any dose:

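### SAP 4.3.1.1 finds medication errors with adverse reactions only by SMQ preferred term, so an accidental overdose recorded under its reaction term could be missed by this secondary endpoint

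*SAP*

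**What the plan says.** SAP 4.3.1.1 defines the endpoint through coded terms: "Medication errors associated with adverse reactions are defined as the AEs whose preferred terms belong to the Standardised MedDRA Queries (SMQ", the query being the one on medication errors, and the AEs must also be "leading to adverse reactions". It does not say whether the narrow or broad scope applies. SAP 4.3.2 summarizes the endpoint in the Randomized Safety Set (RSS) by period and overall for each method, and adds a by-participant listing of errors with their related reactions.

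Protocol 8.5 brings overdose into the concept: "Unintentional overdose events are considered Medication Errors and should be reported as described in Section 8.3.7 and Section 8.3.8". Appendix 3, in the list of events meeting the AE definition, says what is entered as an AE. Reportable are: "Signs, symptoms, or the clinical sequelae of a suspected overdose of either study medication or a concomitant medication". It then adds: "Overdose per se will not be reported as an AE/SAE unless it is an intentional overdose taken with possible suicidal/self-harming intent".

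Medication errors also have their own records. Under Protocol 8.3.7 they "shall be recorded in the paper Medication Error form by the investigator". An error with an adverse reaction is an adverse event of special monitoring (AESM), and 8.3.7 continues: "Medication errors that are considered AESM (see Section 8.3.8) will be recorded and reported within 24 hours following the SAE recording and reporting procedures". Section 8.3.8 repeats the requirement: "Medication error associated with adverse reaction(s) should also be assessed, recorded, and reported using the Medication Error form as indicated in Section 8.3.7".

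SAP 4.5.2 names this event type among the AESMs, identifies AESMs by the investigator's yes/no answer in the CRF, and tabulates them by type. It does not say where the type comes from.

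**The concern.** The endpoint search looks only at the preferred term of the AE record. The overdose text in Appendix 3 directs the site to record the clinical consequence rather than the overdose. If a site does that, the error is held in the AESM flag and on the paper form, and the AE dataset holds only a reaction term. A search on error terms has nothing to match.

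The endpoint bears directly on unsupervised home dosing, and few events can be expected to decide how it reads: one case is the difference between reporting none and reporting some. In the overdose situation the rule can only lower the count. The AESM table in SAP 4.5.2, also produced for the RSS by period and method, could then show a case that the endpoint table does not, and neither section provides for comparing the two.

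**Working it through.** The plan gives no expected rate or precision for this endpoint, so there is no figure to reproduce. The check is a comparison of passages, followed by simple proportions for scale.

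**Tracing one hypothetical case.** A participant unintentionally takes too much at a home visit and then has a reaction.

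1. Is it a medication error? Yes, by Protocol 8.5.
2. Does it belong to the endpoint concept? Yes. It is an error with harm, which Appendix 12 classes as an error associated with adverse reaction(s) and 8.3.8 lists as an AESM.
3. What is entered as an AE? Appendix 3 requires the reaction and says the unintentional overdose itself is not an AE. Sections 8.3.7 and 8.3.8 send the error through SAE recording, and Appendix 3 puts SAE information in the CRF. A site could therefore (A) enter the reaction only, or (B) also enter the error as an event.
4. Does SAP 4.3.1.1 find it? Under A, the only term is the reaction's, so an error-term search may not find it. Under B, it is found if the term entered codes into the SMQ. The clause on leading to adverse reactions narrows the set and adds no case.
5. Does SAP 4.5.2 find it? Under A or B, yes, if the investigator answers yes to the AESM question.
6. Does the Medication Error form hold it? Yes, if completed as 8.3.7 and 8.3.8 require.

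So under A the same event can be in the AESM table and on the form, yet absent from the endpoint.

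**Scale.** The number missed is an assumption: one participant. The change in the percentage is 100 × 1/n.

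| Denominator | n | Source | Change (points) |
|---|---|---|---|
| Overall, one method | 30 | planned number, Protocol 9.9 | 100/30 = 3.3 |
| Overall, one method | 31 | just above plan | 100/31 = 3.2 |
| Overall, one method | 75 | all screened randomized (ceiling) | 100/75 = 1.3 |
| One period-by-method cell | 15 | planned minimum per sequence | 100/15 = 6.7 |
| One period-by-method cell | 37 | smaller half of 75 (37 + 38) | 100/37 = 2.7 |

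The planned 30 refers to participants who self-administer by both methods, whereas this endpoint uses the RSS, which includes everyone randomized and dosed. SAP 4.2.2 says that more participants than planned could use both methods. The overall effect of one case is therefore below 3.3 points.

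**The case against.** The best counter-argument is that Appendix 3 excludes only overdose without consequences. Where there is harm, the specific rules in 8.3.7 and 8.3.8 name the error as the event and send it through SAE recording, so an error term may well reach the CRF. Whether it does depends on material not supplied: the SMQ term list, the CRF Completion Guidelines, the Data Cleaning Plan and the TFL specifications. SAP 4.3.2 plans a listing that pairs errors with reactions, and Protocol 8.4 plans ongoing SAE reconciliation, which plausibly reaches AESMs.

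Much of this stands, and it is why the miss is only possible. It does not remove the point. Reaching the CRF does not fix the preferred term, and a site could reasonably follow either instruction. The listing names no source for its cases. Protocol 8.4 mentions neither the Medication Error form nor a comparison with the SMQ result.

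It can also be said that parallel identification is normal in this SAP, since headache is both an AE of focus by coded term and an AESM by flag. Those are different concepts, though: any headache against severe or serious headache. Here both rules aim at the same event type. Within SAP 4.3.1.1 itself, local site reactions are already identified from the CRF.

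A reader might infer that SAP 4.1.7, which drops data after self-administration stops from this endpoint but keeps them for safety, is a further important reason for the two tables to differ. The documents give little support for that. Appendix 14 describes this AESM as a failure in self-administration, and after stopping, an HCP gives the drug (Protocol 4.1). At most a late reaction to an earlier error would be affected.

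**Conclusion.** The point holds as a possible undercount. As written, the SAP can miss an accidental overdose with a reaction when only the reaction is coded, although the flag and the form should capture it. This rests on three assumptions: that such an event occurs, that the site follows the overdose text in Appendix 3, and that the reaction's term is outside the SMQ. It also rests on a single sentence of Protocol 8.5, whose public text may be incomplete.

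One missed participant would move an overall percentage by between 1.3 and just under 3.3 points, and a period-by-method cell by 2.7 to 6.7 points under the denominators shown.

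Two stronger readings are not supported. The documents do not show that cases will be missed. Nor would a missed case vanish from the safety record: it stays in the TEAE tables and AE listings under its reaction term, and in the AESM table if flagged. The study has no hypothesis test, and no confidence interval is planned for this endpoint. What is at risk is the count for one secondary endpoint, which is worth correcting because the correction is cheap.

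**What to change.** In SAP 4.3.1.1, count a participant if an AE in the Self-administration Periods meets either condition:

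- (a) the investigator flagged it as an AESM of the type medication error associated with adverse reaction(s), with the type taken from the CRF or the Medication Error form; or
- (b) the SMQ finds it and it is linked to an adverse reaction. State the SMQ scope here, as SAP 6.13 does for several other queries.

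Before lock, cross-check SMQ hits, AESM flags and Medication Error forms, and query discrepancies with the site. Use the same rule for the SAP 4.3.2 tables and by-participant listing.

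Leave the AESM table in SAP 4.5.2 on the investigator's answer, and footnote any case found only by the SMQ. Extending the either/or rule to that table would count as AESMs events to which the investigator answered no, contrary to SAP 4.5.2.

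The cost is SAP wording and a small manual reconciliation of records that the protocol already requires.

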## 4.3.2 Main analytical approach

The number and proportion of participants experiencing TEAEs during the Training Period will be summarized overall for the SS. The number and proportion of participants experiencing TEAEs during the Self-administration Periods will be summarized by period and overall for each self-administration method for the RSS. The number and proportion of participants experiencing TEAEs during the Self-administration Periods whatever the self-administration method will also be reported.

The number and proportion of participants experiencing local site reactions up to 24 hours after IMP administration will be summarized:

- overall for the SS
- for the Training period for the SS
- during the Self-administration Periods by period and overall for each self-administration method for the RSS
- during the Self-administration Periods whatever the self-administration method.

The number and proportion of participants experiencing medication errors associated with adverse reactions during the Self-administration Periods will be summarized by period and overall for each self-administration method for the RSS. The number and proportion of participants experiencing medication errors associated with adverse reactions during the Self-administration Periods whatever the self-administration method will also be reported.

A by-participant listing will also be produced including the medications errors together with the related adverse reactions for the RSS. As per the guidance on medication related adverse events (Pharmacovigilance Risk Assessment Committee. Good practice guide on recording, coding, reporting and assessment of medication errors (EMA/762563/2014).

http://www.ema.europa.eu/docs/en\_GB/document\_library/Regulatory\_and\_procedural\_guideline /2015/11/WC500196979.pdf (2015). Accessed 30 Jan 2023.), a medication error is an unintended failure in the drug treatment process that leads to, or has the potential to lead to, harm to the patient. An adverse reaction is a response to a medicinal product which is noxious and unintended (Directive 2001/83/EC, Article 1 (11)). An adverse event which is reported as a consequence of a medication error is considered as an adverse reaction.

# Exploratory endpoints analysis

# Participant's relative preference

The participants' relative preference for subcutaneous infusions performed by an HCP versus self-administration and the manual push method versus the use of a syringe driver for self-administration will be evaluated at Visit 19 ( ) by sequence and overall for the RSS. Participants' preference will also be listed for the RSS.

Rozanolixizumab

#### 4.4.2 MG-ADL

The symptom changes in study participants with gMG will be evaluated. The complete list of MG-ADL items and scores are provided in Table 6-5. The total score will be calculated according to the rules set down in Section 6.11.

itzation The MG-ADL total score and change from Baseline will be summarized at each visit for the RSS by sequence using descriptive statistics.

Worsening in MG-ADL score will be defined by a >2 points increase from Baseline at any timepoint during the treatment period. The number and proportion of study participants experiencing a worsening of their MG-ADL symptoms during the study will be summarized overall for the RSS. This table will also include the number, proportion and 90% CI of study participants experiencing MG-ADL worsening, considering the last available measurement in the study before the End of Study Visit (Visit 21). The 90% CI will be estimated using the Wilson method (without continuity correction) [2].

Since MG-ADL is completed predose, if time of collection is missing for Visit 2, this will be considered as the Baseline assessment.

Line plots of mean MG-ADL total score and mean change from baseline over time by sequence will be presented for the RSS. Spaghetti plots of MG-ADL total score and change from baseline over time will be presented for the RSS.

By-participant listings of MG-ADL values will be provided for the SS.

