8.2.2 Participant's preferred method of rozanolixizumab administration questions

me study participants will be asked to evaluate their relative preference for SC infusions performed by an HCP versus self-administration and the preference for the manual push method versus the use of a syringe driver for self-administration.

Materials supporting the collection of data relating to the participant's preferred method of rozanolixizumab administration are provided in Appendix 16 (Section 10 16)

Self-Injection Assessment Questionnaire (Infusion version) 8.2.3

Myasthenia Gravis Activities of Daily Living

The MG-ADL is an 8-item PRO instrument developed on the basis of the QMG (Wolfe et al, 1999). The MG-ADL targets symptoms and disability across ocular, bulbar, respiratory, and axial symptoms. In a recent study, reliability, validity, and responsiveness of the MG-ADL were further assessed. The questionnaire showed strong construct validity when evaluated against the MG-C as well as against the MG-QOL15r; high test-retest reliability in a 1-week interval; and it was demonstrated that a 2-point improvement indicates clinical improvement (Muppidi, 2012; Muppidi et al, 2011). The total MG-ADL score ranges from 0 to 24, with a higher score indicating more disability (Appendix 17 [Section 10.17]).

Confidential Page 48 of 124 The MG-ADL is being utilized in MG0020 as a parameter of symptom monitoring rather than an assessment of treatment benefit.

Independently of study visit type (site, home, or virtual), the MG-ADL must be completed by study participants in a quiet place by themselves without the help of a partner or caregiver, before any clinical examination takes place. Study participants should be informed of the importance of this questionnaire and instructed to read the items and instructions carefully. They should be informed that there are no correct or incorrect answers.

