9.3.3 Other safety analyses

All other safety analyses will be based on the Randomized Safety Set or Safety Set as appropriate.

To assess the participant's experience with self-administration of SC infusions, a within-participant assessment of treatment success or nonsuccess with self-administration with the syringe drive or manual push will be tabulated through the use of a 2x2 table presenting the number and proportion of participants in each category. The last dose in each of the Self-administration Periods will be considered. The tabulation will be presented by sequence and overall.

The number and proportion of participants who achieved a successful self-administration at each of the 3 home self-administration visits will be tabulated separately for each self-administration method.

The participant's relative preference for SC infusions performed by an HCP versus self-administration as well as the preference for self-administration using the manual push method versus the use of a syringe driver will be summarized by sequence and overall.

The PRE-SIAQ (Infusion version) domain scores will be summarized at Baseline by sequence and overall. The POST-SIAQ (Infusion version) will be summarized for each self-administration method.

The change from Baseline MG-ADL score will be summarized by visit and period. Worsening in MG-ADL score will be defined by a ≥ 2 points increase from Baseline. Baseline value will be defined for each period separately. The number and proportion of study participants experiencing a worsening of their MG-ADL symptoms during the Self-administration Period will be summarized for each self-administration method. The proportion of worsening together with its 90% CI for each self-administration with syringe driver and manual push will be estimated considering the period and sequence as fixed effects and participant as a random effect to encompass the within-participant correlation.

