4.4.2 MG-ADL	
 
Specified worsening in MG-ADL score will be a ≥2 point increase from Baseline at any timepoint during the treatment period. Added that MG-ADL worsening at the last available measurement of MG-ADL before the EOS Visit (Visit 21) would be presented in this table and a 90% CI estimated using the Wilson method.
 
Stated that if time of collection is missing for MG-ADL at Visit 2, this will be considered as the Baseline assessment.
 
Specified MG-ADL will be summarized at each visit by self-administration method.
 
Line plots of mean MG-ADL total score and mean change from baseline over time added. Spaghetti plots of MG-ADL total score and change from baseline over time also presented.
 
	
 
Aligns with the definition of MG-ADL worsening in the Protocol. MG-ADL worsening at the last available timepoint before EOS will be presented and a 90% CI calculated as specified in the Protocol.
 
If time of collection for MG- ADL at Visit 2 is missing, this can be assumed as the Baseline assessment as MG-ADL is collected predose per Protocol.
 
As the MG-ADL summary is split by sequence and visit, additionally splitting by self- administration method is not required.
 
Plots added to visualize MG- ADL changes over time.
 

Section # and Name	Description of Change	Brief Rationale
4.4.3 Pharmacodynamic	For the RSS, observed values and percentage change from baseline will be summarized by sequence. Specified that if rescue therapy is taken, IgG values collected 8 weeks after the start of rescue medication will not be included in summary analysis. Line plots of median IgG concentrations and percentage change from baseline over time added. Spaghetti plots of IgG concentrations and percentage change from baseline over time will also be presented. A line plot presenting mean change from baseline in MG- ADL and median percentage change in IgG by sequence will be produced. Plots of individual percentage change from baseline in IgG concentrations and change from baseline in MG-ADL total score added. Specified IgG laboratory assessments are performed predose.	To provide a clearer picture of participants' IgG levels throughout the study. IgG values may be affected by rescue therapy use and influence analyses. Plots added to visualize IgG changes over time.

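### SAP 4.4.2 as printed sets MG-ADL worsening at more than 2 points, protocol 9.3.3 at 2 points or more, and SAP 4.8 declares no change: probably a slip, to be checked and corrected

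*SAP*

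**What the plan says.** Protocol 9.3.3 gives the definition: "Worsening in MG-ADL score will be defined by a ≥ 2 points increase from Baseline".

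SAP 4.4.2 gives the operative sentence for the analysis: "Worsening in MG-ADL score will be defined by a >2 points increase from Baseline", at any timepoint in the treatment period. Two summaries depend on it, both in one table for the Randomized Safety Set:

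- the number and proportion of participants "experiencing a worsening of their MG-ADL symptoms during the study will be summarized overall for the RSS";
- the number, proportion and 90% CI of those "experiencing MG-ADL worsening, considering the last available measurement in the study before the End of Study Visit (Visit 21"), with the interval by the Wilson method without continuity correction.

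SAP Section 1 says that changes from the protocol analyses are documented in Section 4.8. For MG-ADL, Section 4.8 records a single study baseline in place of period-specific ones, and reporting by sequence. It does not mention the threshold.

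The SAP version history, in its Amendment 1.0 entry for Section 4.4.2, describes this sentence as follows: "Specified worsening in MG-ADL score will be a ≥2 point increase from Baseline at any timepoint during the treatment period". The reason given there is: "Aligns with the definition of MG-ADL worsening in the Protocol".

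**The concern.** The two documents differ by one sign, and the sign decides who counts as worsened. SAP 6.11 builds the MG-ADL total from 8 items scored 0 to 3, so totals are whole numbers unless an item is imputed. For complete questionnaires, more than 2 points therefore means at least 3.

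The programmer works from SAP 4.4.2. Nothing in Section 4.8 signals that the protocol threshold still applies, so a literal derivation would follow the stricter rule. MG-ADL worsening stands among the protocol's safety analyses as symptom monitoring under self-administration. The stricter rule can only make that summary look more favourable, and the report would not disclose a departure from the protocol.

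**Working it through.** The documents state no expected worsening rate, sample size or power for this endpoint, so there is no figure of the plan's own to reproduce. As a check on the interval code only, exact 90% Clopper-Pearson limits for 24, 27 and 29 successes out of 30 come to 64.3–90.9, 76.1–97.2 and 85.1–99.8. These match protocol Table 9-1.

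**Step 1: where the rules differ.** Both rules were applied to every change score from −24 to +24 in steps of 0.1. The fine step allows for SAP 6.11, under which imputed items are rounded to one decimal place. The rules disagree at one value only, +2.0.

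**Step 2: who is affected.**

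| Participant | Any-timepoint proportion | Last-available proportion |
|---|---|---|
| Largest increase exactly 2 | lost under >2 | lost only if the last value is also at +2 |
| +2 at one visit, above 2 at another | still counted | lost only if the last value is at exactly +2 |
| Largest increase above 2, last value above 2 | counted | counted |
| Never reaches +2 | not counted under either rule | not counted under either rule |

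**Step 3: direction.** Let N be the number of participants, k the number counted under >2, and m the number at exactly +2 on the relevant measure (largest value or last value). The proportion is k/N under >2 and (k + m)/N under ≥2. The difference is m/N, which is never negative, so the stricter sign can lower the reported worsening but never raise it.

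**Step 4: illustration.** The counts are assumed and do not come from the documents. Take N = 30 and k = 3. The Wilson interval with p = x/N and z = 1.645 is

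[p + z²/(2N) ± z·√(p(1−p)/N + z²/(4N²))] / (1 + z²/N).

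For x = 3, p = 0.100 and z² = 2.706. The centre is (0.100 + 0.0451)/1.0902 = 0.133 and the half-width is 1.645 × √(0.00300 + 0.00075)/1.0902 = 0.092. The limits are 4.1% and 22.6%. The other rows follow in the same way:

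| m at exactly +2 | Counted under ≥2 | Proportion | 90% Wilson CI |
|---|---|---|---|
| 0 | 3 | 10.0% | 4.1 to 22.6 |
| 1 | 4 | 13.3% | 6.1 to 26.6 |
| 3 | 6 | 20.0% | 10.7 to 34.3 |
| 6 | 9 | 30.0% | 18.4 to 44.9 |

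Under >2, every row would report the first line. In SAP 4.4.2 the interval is planned with the last-available proportion, so for the any-timepoint proportion only the point estimates apply.

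**The case against.** The strongest answer is that nobody planned a stricter threshold. The version history describes the sentence with ≥2 and states the aim of matching the protocol, which would also explain why Section 4.8 lists no threshold change. A change log is not operative text, and a difference from it is not itself an error. As evidence of intent, however, it is clear.

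The sign may also have been damaged when the PDF was read. In SAP 6.4 the top weight category is printed as >100kg after 70 to <100, which leaves exactly 100 kg unclassified, although the dosing tier in protocol Table 1-2 is ≥100kg. One age grouping there is printed as <18, 19 to <65 and >65, which leaves 18 and 65 without a place. Against this, ≥ survives in SAP 1.2, 4.5.1 and Tables 6-3 and 6-4, and in Table 6-4 it stands beside a genuine >200ms. The supplied text cannot settle the matter; the source file can.

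The consequences are limited too. The endpoint is exploratory, the study tests no hypothesis, and protocol Section 8.2 uses MG-ADL to monitor symptoms, not to assess treatment benefit. Totals and changes are also summarized by visit, plotted by participant and listed, so 2-point increases stay visible.

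All of this stands. It lowers the severity and makes a check of the source the first step. It does not remove the conflict between the two operative sentences as printed.

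**Conclusion.** As printed, SAP 4.4.2 and protocol 9.3.3 define worsening differently and the difference is undeclared. The likeliest explanation is a slip or a lost bar. If the source SAP does read >2 and is programmed that way, each proportion falls by m/N. That amount cannot be computed, because the documents give no distribution of MG-ADL changes; it is zero if nobody is at exactly +2.

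Four stronger readings are tempting, and the documents do not support them:

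- *That the sponsor chose a more favourable threshold.* The version history points the other way.
- *That every 2-point increase drops out of both proportions.* For the any-timepoint proportion, only participants whose largest increase is exactly 2 are lost.
- *That the protocol calls a 2-point worsening clinically relevant.* What it reports is that "it was demonstrated that a 2-point improvement indicates clinical improvement", and it makes no such statement about deterioration.
- *That the loss can be put at a particular percentage.* Any such figure rests on an assumed mean, spread and correlation of changes.

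The severity is minor. No primary or secondary result, test or sample-size argument is affected.

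**What to change.** Check the sign in the source SAP.

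- If it reads ≥2, the text needs no change; confirm only that the program uses ≥2.
- If it reads >2, change Section 4.4.2 to ≥2 to match protocol 9.3.3. State that the same threshold governs the last-available proportion, which does not restate it, and check the programmed derivation of both proportions.
- If >2 was in fact intended, list the change in Section 4.8 with a reason.

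The cost is one character, one clarifying sentence and a check of one derivation. The reported worsening proportion may rise slightly as a result.
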